10. ENDPOINTS

- *Describe the primary and secondary study endpoints*
- *Describe any primary or secondary safety endpoints*

The endpoint of this study is provider adoption of the PERK tool. Secondary outcomes include increased CTPA yield [% of positive tests], and decreased CTPA ordering.

Our primary feasibility outcome is post-pilot provider satisfaction.

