In AIM 2, we will perform iterative usability testing of an evolving prototype of "PERK". We will build the prototype into the wireframing tool, Axure. The PERK prototype will add 4 small nudges to PE CALC. Usability of the prototype will be tested in two steps, "Think Aloud" and "Near Live" (n=5 participants each). During "Think Aloud" testing, participants verbalize their thought processes while interacting with the prototype. Participants will be given written clinical scenarios with low, intermediate, or high probability PE cases and asked to complete the specific steps necessary to use the tool. During

“Near Live” testing, participants will interact with a standardized patient pretending to have a low, intermediate, or high probability of PE. Participants will use the tool as they would during a real patient encounter to highlight higher level workflow usability issues.

All five participants for each round of testing will interact with the prototype at each step. The tool will be modified after “Think Aloud” and again after “Near Live” based on testing results. Before every session participants will be asked to complete a questionnaire to gather demographic information. They will be given a laptop with the PERK prototype and screen capture software. After every session they will complete a questionnaire to collect retrospective impressions of the tool, and a quantitative survey, the System Usability Scale. Each session will be audio-taped and Morae usability testing software will be used to screen-capture record all human-EHR interactions.

AIM 2 participants will be tested either in person or remotely via videoconferencing (such as with Microsoft Teams). Participants being tested remotely will fill out consent forms, the Audio Visual Authorization Form, and the surveys on REDCap. Participants being tested in person will be given the option to fill out these forms on REDCap or on paper. Audio and screen capture recordings (using Hypercam, Teams, or Morae) will be taken for each session. Prior to or at the beginning of each session, participants will fill out the Usability Pre-session Questionnaire. At the end of each session, participants will verbally answer questions from the Post-session Interview and PERK Tool (Feedback Survey Aim 2) documents; they will also fill out the System Usability Scale (on REDCap for remote testing, on paper or REDCap for in-person testing).

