In AIM 3, we will conduct a pilot trial to evaluate the feasibility, acceptability, and preliminary efficacy on provider adoption of the new tool, “PERK”, compared to the current PE CALC tool. This will consist of a six month prospective cohort pilot study with a retrospective cohort control group. All full time ED providers at NSUH and LIJMC will be eligible for participation. Training on PERK use will be conducted as a presentation during ED Grand Rounds. This will be led by [name] and a research coordinator. It will last about 30 minutes with three basic components: 1) overview of the evidence supporting tool use, 2) hands-on session to practice using the tool, and 3) question and answer session. Similar educational training was conducted before launching the current tool, PE CALC.

For the pilot study, we will use EHR reporting data to generate a PERK monitoring dashboard. The dashboard will include trigger rates (percentage of ED patients for which the tool triggers), adoption rates (the percentage of times the provider completes the calculator once the tool is triggered), CTPA order rates (percentage of total ED patients for which a CTPA is ordered for the evaluation of PE), and CTPA yield (the percentage of tests ordered to evaluate for PE that are positive for PE).

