For AIM 3, we will determine the feasibility of PERK using post-pilot provider satisfaction surveys, where mean scores for each response on a Likert scale will be reported with standard deviations and 95% confidence intervals. Acceptability will be determined from post-pilot stakeholder interviews with providers, nurses and the ED chairs at both institutions. Preliminary efficacy will be assessed by comparing provider adoption of PERK to provider adoption for the first six months of PE CALC. Providers in the pre- and post- groups will be summarized using descriptive statistics. Provider age, gender, race and type (attending vs. resident vs. physician assistant) will be compared between the two groups using two-sample t-test or Wilcoxon Rank Sum test for continuous variables and Chi-squared or Fisher's exact test for categorical variables. Since the variability of the adoption rate of PERK for each provider depends, in part, on the number of encounters, providers with larger numbers of encounters should carry more weight. Therefore, a weighted two-sample t-test will be used to test the difference in the weighted means of adoption rates between the groups. Weighted least squares linear regression with number of encounters as weight for each observation (provider) will be performed, to see whether there is difference in the adoption rate between the two groups after controlling for provider age, gender, race, type and other confounding variables.

Power Calculations: We expect 150 providers who meet the inclusion criteria to be in each of pre- and post- groups. We also assume the mean adoption rate of the pre group to be 15% with the standard deviation of 10% based on the historical data, and the mean adoption rate of the post- group to be 20%, 25% and 30% with equal standard deviation. With the sample size of 150 in each group, there will be at least 99% power to detect the difference of 5%, 10% and 15% in the mean adoption rates using a two-sided two-sample t-test at a significance level of 0.05. We are aware that the weighted two-sample t-test should be used to calculate the power. However, due to the lack of information about weights, the unweighted two-sample t-test was used instead.

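### Adoption rates are weighted by an undefined count of encounters although their denominator is triggers, and under either reading the weighted test needs a variance that allows for real differences between providers

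*Combined protocol and SAP*

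**What the plan says.** Section 10 names the efficacy endpoint: "The endpoint of this study is provider adoption of the PERK tool". The only operational definition is in the dashboard description in section 11: "adoption rates (the percentage of times the provider completes the calculator once the tool is triggered". A provider's rate is therefore completions divided by triggers. The same list defines "trigger rates (percentage of ED patients for which the tool triggers", so triggers are a subset of ED patients and the plan treats the two as separate counts.

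Section 12 (Aim 3) argues that "the variability of the adoption rate of PERK for each provider depends, in part, on the number of encounters", concludes that "providers with larger numbers of encounters should carry more weight", and specifies a weighted two-sample t-test. For the adjusted analysis it says: "Weighted least squares linear regression with number of encounters as weight for each observation (provider) will be performed". Encounters is not defined there. The only other use of the word, in the Aim 2 usability testing, is for a patient visit: "Participants will use the tool as they would during a real patient encounter".

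The power calculation uses no weights and says so. It takes 150 providers per group, means of 15% against 20%, 25% or 30%, and an SD of 10%.

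**The concern.** The sampling error of completions over triggers depends on the number of triggers. A weight justified by that sampling error should be the trigger count, but the plan names encounters and does not connect the two. Two analysts could follow section 12 correctly and report different primary estimates, one weighting by all ED visits and the other by triggered visits.

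The second issue applies whichever count is meant. A weighted t-test or weighted least squares with its usual variance treats each provider's variance as proportional to 1/weight. That would hold if binomial noise were the only source of variation. The plan's own SD of 10% suggests that providers also differ in their true rates, so the standard error for H2 can be too small.

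**Working it through.** **Inputs.** From section 12: 150 per group, 15% against 20%, SD 10%, two-sided 5%. From section 11: rate r = C/T (completions over triggers) and trigger rate t = T/E (triggers over ED patients). The documents give no values for E, T or t, so every count below is an assumption.

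**1. The plan's power figure.** The noncentrality is 5 / (10 × √(2/150)) = 4.33 on 298 df, giving 99.1% power. For 10 and 15 points it exceeds 99.99%. The stated figure of at least 99% reproduces, and the weight does not enter it.

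**2. What each weight averages.**
- Trigger weights: ΣT(C/T) / ΣT = ΣC / ΣT, the pooled completions per trigger.
- Encounter weights: ΣE(C/T) / ΣE.
- Since T = E·t, the trigger-weighted mean equals the encounter-weighted mean plus Cov(t, r) / mean(t), with covariance and mean both encounter-weighted.

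The two means therefore agree if t is constant or unrelated to r. The pre/post difference moves only if that gap changes between periods.

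Example (assumed): provider A has 1000 patients, 10 triggers and 10% adoption; provider B has 200 patients, 40 triggers and 30% adoption.
- Encounter-weighted: (1000×0.10 + 200×0.30)/1200 = 13.3%.
- Trigger-weighted: (1 + 12)/50 = 26.0%.
- Unweighted: 20.0%.

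If encounters means triggered encounters, the planned mean is already 26.0%.

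**3. The difference.** Take a deliberately extreme case (assumed): all providers have 600 encounters, half with 6 triggers and half with 54.
- A uniform gain gives the same difference under both weights.
- A 10-point gain only in the low-trigger half gives 0.5×10 = +5 points with encounter weights and 6×10/60 = +1 with trigger weights.
- A 10-point gain only in the high-trigger half gives +5 and 54×10/60 = +9.

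**4. The variance.** With true between-provider variance τ², Var(r) is approximately τ² + p(1−p)/T. At p = 0.15 the binomial parts are 0.1275/6 = 0.0213 and 0.1275/54 = 0.0024, a 9-fold ratio. If the plan's 10% is read as the between-provider SD, τ² = 0.010. The totals are then 0.0313 and 0.0124, a ratio of about 2.5. Trigger weights of 1:9 are then not inverse-variance weights, and equal encounter weights are not either.

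**5. Simulation.** Assumptions: 150 per group, between-provider SD 10%, mean 600 encounters (CV 0.6), mean trigger rate 5%, uniform 5-point effect, 400 runs per scenario. Type I error is for the model-based weighted t-test with both groups at 15%.

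| CV of trigger rate | Correlation with adoption | Encounter-weighted pre/post | Trigger-weighted pre/post | Type I error, encounter / trigger |
|---|---|---|---|---|
| 0 | 0 | 15.0 / 19.9 | 15.0 / 20.0 | 5.8% / 5.8% |
| 0.5 | 0 | 15.0 / 20.0 | 15.1 / 20.0 | 9.2% / 10.2% |
| 1.0 | −0.5 | 14.9 / 19.8 | 11.3 / 16.2 | 6.2% / 12.8% |
| 1.0 | 0 | 15.0 / 19.9 | 15.0 / 19.9 | 4.8% / 17.0% |
| 1.0 | +0.5 | 15.0 / 20.1 | 19.1 / 24.3 | 7.5% / 21.8% |

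The simulation error on type I error is about 1–2 points. Over all nine scenarios, type I error was about 5–9% with encounter weights and 6–22% with trigger weights. A further set with the total SD near 10% gave about 4–11% and 5–20%, against about 4–7% with a robust variance.

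**The case against.** The strongest reply is that encounters may mean encounters in which the tool triggered. The variance rationale fits that reading, and the weight is then already the rate's denominator. This stands as a possible reading. It leaves a gap in the wording, because section 12 does not say so and section 11 has its own term for triggers.

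A reader might infer that the tested mean is not the adoption outcome the plan defines. The documents do not support that. Under either weight, each provider's rate is completions over triggers; only the averaging across providers differs. Neither section 10 nor H2 in section 4 says whether the target is the pooled rate or the rate of an average provider.

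A reader might also infer that the two weights could give opposite signs. That would need the tool to help some providers and harm others, in line with their trigger load. Nothing in the documents indicates this, and the cases above keep the same sign.

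It is also fair to say that the H2 difference stayed near 5 points in every simulated scenario. Those scenarios apply a uniform effect, which largely fixes the difference in advance. Alert burden is one of the barriers named in section 4, so an effect that varies with trigger load is plausible but not shown. The 6-against-54 illustration is extreme, and the documents give nothing to place the real spread.

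Finally, this is a pilot of preliminary efficacy, and section 12 admits that it lacks information about the weights. That limits how much rests on the test. It does not remove the need to define the weight before analysis.

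**Conclusion.** The concern holds in limited form. Read literally, the weight in section 12 does not match its own justification, because section 11 makes triggers the denominator. If all ED visits are meant, the weighted mean can differ from completions over triggers. The H2 difference is affected only if trigger rate varies between providers and is related to adoption or to the tool's effect. Its size cannot be computed from the documents. If triggered encounters are meant, the weight is right and the wording is not.

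The variance problem remains under both readings and matters more for the test. The inflation depends on the assumed trigger distribution and on how much of the plan's 10% SD is true variation between providers. It was small where weights varied little and largest with trigger weights and a widely varying trigger rate. Changing the weight alone could therefore make the test worse.

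**What to change.** In section 12, replace the number of encounters by the number of times the tool triggered for that provider in the period, for both the weighted t-test and the weighted regression. The unadjusted weighted mean is then total completions over total triggers. If an average-provider rate is intended instead, the plan should say so and choose the weight to match.

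In the same edit, specify a heteroscedasticity-robust (sandwich) variance for both analyses, or replace them with a beta-binomial or provider random-effect model. The weight change should not be made without the variance change.

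The cost is a few sentences and no new data, since trigger counts are already needed to compute each rate. Intervals will be slightly wider. Precision may be somewhat lower than with encounter weights if variation between providers dominates. The change should be made before outcome data are examined.

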AIM 2: To conduct iterative usability testing on an evolving prototype of a new tool, “PERK”. This will involve both qualitative and quantitative assessments of ease of use of “PERK”. We will perform “think aloud” and “near live” testing to develop a prototype that will be revised and evaluated.

AIM 3: To evaluate the feasibility, acceptability and preliminary efficacy on provider adoption of a new tool compared to the current tool, in a pilot trial. We will conduct a 6 month pre-post analysis of “PERK” by comparing it to retrospective data from the first 6 months of PE CALC. Our primary feasibility outcome is post-pilot provider satisfaction. Secondary outcomes include stakeholder acceptability.

***H1:** PERK will demonstrate higher rates of provider satisfaction as compared to PE CALC.* Our primary efficacy outcome is increased provider adoption. Secondary outcomes include increased CTPA yield [% of positive tests], and decreased CTPA ordering. ***H2:** “PERK” will demonstrate higher provider adoption as compared to PE CALC.*

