5. RESOURCES AVAILABLE TO CONDUCT THE HUMAN RESEARCH

- *Explain the feasibility of meeting recruitment goals of this project and demonstrate a potential for recruiting the required number of suitable subjects within the agreed recruitment period*
 - *How many potential subjects do you have access to?*
- *Describe your process to ensure that all persons assisting with the trial are adequately informed about the protocol and their trial related duties and functions*

The study will collect data from the Emergency Departments (ED) of both North Shore University Hospital (NSUH) and Long Island Jewish Medical Center (LIJMC). Eligible participants for all three aims will be medical doctors and physician assistants working full time in either of these Emergency Departments (86 eligible at NSUH; 63 eligible at LIJMC). We will recruit from within this pool for AIM 1 and AIM 2. For AIM 3, all eligible providers will be automatically enrolled, as we will be collecting data from the EHR regarding the use of PERK.

All persons assisting with the trial will review the research protocol and be informed of their specific duties prior to the commencement of any research activities. We will also hold a study launch meeting for all involved in the research.

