6. RECRUITMENT METHODS

- *Describe the source of potential subjects*
- *Describe the methods that will be used to identify potential subjects*
- *Describe any materials that will be used to recruit subjects. A copy of any advertisements (flyers, radio scripts, etc.) should be submitted along with the protocol.*
- *If monetary compensation is to be offered, this should be indicated in the protocol*

Eligible subjects for all three aims of this study will be medical doctors and physician assistants working full time at NSUH or LIJMC. This includes residents in the Emergency Medicine/Internal Medicine program.

For AIM 1, potential subjects will be identified using the Electronic Medical Records (EMR) based on PE CALC use. We will contact participants via our secure email system. We will inform participants about the study, offering a \$50 reimbursement for their time.

In addition, we will contact department heads at NSUH and LIJMC, as well as administrators, attendings, chief residents, administrative residents, and head PAs, and request names of potential participants for Aims 1 and 2. We will email the identified providers, mentioning the person who recommended that they might be interested in participating, and asking if they would like to participate in our study. Alternatively, we will ask department heads, administrators, or other faculty or staff to email potential participants and inform them of our study. We may also present our study at ED faculty meetings and/or resident meetings to raise awareness of our study. Alternatively, we will ask department heads, administrators, or other faculty or staff to present our study in information sessions to promote participation.

For AIM 2, eligibility and recruitment methods will be the same as for AIM 1, as indicated in the previous paragraph. We will contact participants using the health system email. We may also ask department heads, administrators, or other faculty or staff to distribute and/or display flyers to promote our study. The flyer may also be distributed through the physician Teams chat. We will inform potential participants and solicit interest, offering a \$50 reimbursement for their time. There may be one follow-up phone call.

For AIM 3, full time ED providers will be eligible. We will conduct a pilot trial of PERK among 150 Emergency Medicine providers at NSUH and LIJMC. We expect 150 providers who meet the inclusion criteria to be in each of the pre- and post-groups.

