8. NUMBER OF SUBJECTS

- *Indicate the total number of subjects to be accrued locally. If applicable, distinguish between the number of subjects who are expected to be pre-screened, enrolled (consent obtained), randomized and complete the research procedures.*
- *If your study includes different cohorts, include the total number of subjects in each cohort.*
- *If this is multisite study, include total number of subjects across all sites*

For AIM 1, we expect to recruit 12 participants to complete semi-structured interviews; however, we will recruit until thematic saturation is achieved.

For AIM 2, we expect to recruit 10 participants (5 for “think aloud” testing; 5 for “near live” testing); however, we will recruit until thematic saturation is achieved.

For AIM 3, we expect to include 150 providers who meet the inclusion criteria in the prospective cohort pilot study, and 150 in the retrospective cohort control group.

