During the first half of Year 3, we will develop the new PERK tool. In the second half of Year 3, we will recruit for the pilot clinical trial in AIM 3. The new PERK tool will be active for 6 months, and all full-time employed providers working in the emergency department at NSUH and LIJMC will be eligible for participation. We will perform the pilot trial in Year 4. The clinical decision support tool will be integrated into the electronic medical record and will be accessible for all full-time employed emergency department providers (n=150). Providers will be trained on using the tool through 30 minute sessions delivered during emergency department grand rounds. Additional education sessions will be delivered to continue participant engagement over time. In the second half of Year 4, to assess feasibility, providers will be contacted by email to participate in a post-pilot satisfaction survey. Reminder emails to complete the survey will be sent out up to five times. To assess acceptability, providers will be contacted by email to participate in one-time stakeholder interviews. A follow up phone call will be conducted with providers to provide participant information and solicit interest. The pilot trial will end in June 2022. We will complete our analyses in the first quarter of Year 5. The anticipated end date for this grant is August 31st, 2023.

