24. WAIVER OR ALTERATION OF THE CONSENT PROCESS

Complete this section if you are seeking an alteration or complete waiver of the consent process.

- *Describe the possible risks of harm to the subjects involved in this study and explain why the study involves no more than minimal risk to the subject:*
- *Explain why the waiver/ alteration will not adversely affect the rights and welfare of subjects*
- *Explain why it is impracticable to conduct this research if informed consent is required*
- *If appropriate, explain how the subjects will be provided with additional pertinent information after participation. If not appropriate to do so, explain why.*

For AIM 3, in which we will collect pilot data on the feasibility, acceptability, and preliminary efficacy on provider adoption of the PERK tool, we are requesting a waiver of informed consent. A waiver of informed consent will be necessary in order to have the PERK tool activated in the EMR profiles of the providers.

The research involves no more than minimal risks to the subjects: The study as described in the proposal would be considered a minimal risk study because it involves collection of de-identified aggregate data from the EHR at the NSUH and LIJMC Emergency Departments.

The waiver or alteration will not adversely affect the rights and welfare of the subjects: Due to the functionality of the tool, providers will be offered the tool and have the ability to dismiss the tool. Use of the tool will not affect employment status of the providers at the clinical site/hospital/health system. We will hold an information session for providers regarding the research study and their participation.

The research could not practicably be carried out without the waiver: The primary objective of AIM 3 is to assess the feasibility, acceptability, and preliminary efficacy on provider adoption of PERK compared to the current PE CALC tool in a pilot trial. In order to study this, all patients assessed for PE must be included. The decision support is completely computerized and will be done in real time. It would not be possible or practical to obtain consent from every provider in the Emergency Departments of NSUH and LIJMC prior to their use of the PERK.

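### Aim 3 compares the same two EDs before and after, so many providers probably appear in both groups, yet every comparative test named assumes independent samples.

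*Combined protocol and SAP*

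**What the plan says.** Section 4 (Aim 3) sets up a six-month pre-post analysis of PERK "by comparing it to retrospective data from the first 6 months of PE CALC". Section 3 places PE CALC in the EDs of NSUH and LIJMC, and Section 11 runs the PERK pilot in the same two departments. Sections 6 and 7 apply one eligibility rule to all aims: full-time doctors and physician assistants at either site. Section 5 gives the pool as "86 eligible at NSUH; 63 eligible at LIJMC". Section 8 states: "we expect to include 150 providers who meet the inclusion criteria in the prospective cohort pilot study, and 150 in the retrospective cohort control group".

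For the efficacy comparison, Section 12 states: "Therefore, a weighted two-sample t-test will be used to test the difference in the weighted means of adoption rates between the groups". For the adjusted analysis: "Weighted least squares linear regression with number of encounters as weight for each observation (provider) will be performed". Provider characteristics are compared with two-sample t or rank-sum tests and chi-squared or Fisher tests, and the power calculation uses an unweighted two-sample t-test. The only limitation acknowledged there is the lack of information about weights.

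No section says how many providers will be in both periods, or mentions linkage, pairing, mixed models, GEE or cluster-robust errors.

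**The concern.** Each group is close to the whole eligible staff of the same two departments. A provider who worked there in both periods supplies two adoption rates, and these are likely to be correlated because willingness to use a decision tool is partly a personal habit. A two-sample test, or a regression that counts those two records as unrelated, uses the wrong variance for the difference.

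This affects the primary efficacy outcome. In a pilot, the estimate and its confidence interval are the main product carried forward, so a wrong interval matters even when power is ample. There is also a question of interpretation. Without linking providers across periods, the report cannot show whether the same people changed their behaviour or the staff changed.

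**Working it through.** **Inputs from the plan.** Pool 86 + 63 = 149 (Section 5). From Section 12: n = 150 per period, pre-period mean 15%, SD 10%, differences of 5, 10 and 15 points, two-sided 0.05.

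**Inputs assumed, because the documents do not give them.** Overlap fraction f, within-provider correlation r, and the number and spread of encounters per provider.

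**1. The plan's own figure.** Independent SE = 10 × √(2/150) = 1.155 points. For a 5-point difference (standardised 0.5), power is 99.1%; for 10 and 15 points it exceeds 99.99%. The statement of at least 99% reproduces.

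**2. Unweighted test with overlap.** True SE = 1.155 × √(1 − f·r). Actual type I error = 2 × [1 − Φ(1.96/√(1 − f·r))].

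| f | r | True SE (points) | Actual type I error |
|---|---|---|---|
| 0.5 | 0.3 | 1.065 | 3.4% |
| 0.7 | 0.3 | 1.026 | 2.7% |
| 0.7 | 0.5 | 0.931 | 1.5% |
| 1 | 0.5 | 0.816 | 0.6% |

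The last row is an upper bound on overlap. Binomial noise also limits r. With a total SD of 10% at a mean of 15%, and m encounters per provider, r cannot exceed [(0.01 − 0.1275/m)/(1 − 1/m)]/0.01. That is 0.38 at m = 20 and 0.59 at m = 30, so the rows with r = 0.5 need more than 20 encounters per provider.

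**3. Planned encounter-weighted test.** Assume a between-provider SD of true adoption of 10% (variance B = 0.01), a mean of 30 encounters, and binomial variance W = (0.1275 − 0.01)/30 = 0.003917. Let ρ = 0.5 be the correlation of a returning provider's true rates, and let returning providers keep their encounter counts, which have coefficient of variation CV.

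- SE the planned test estimates: √[(2/150)(B + W)] = 1.36 points at every CV.
- True SE: √{(2/150)[B(1 + CV²)(1 − f·ρ) + W]}. At f = 0.7 this is 1.18, 1.27 and 1.50 points for CV 0, 0.5 and 1.
- Actual type I error = 2 × [1 − Φ(1.96 × planned SE/true SE)].

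The table gives this formula's result, then in brackets the rejection rate from 3,000 simulated null trials per cell (Monte Carlo error about 0.4 points).

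| f | CV 0 | CV 0.5 | CV 1 |
|---|---|---|---|
| 0 | 5.0% (5.8%) | 7.1% (6.1%) | 13.5% (13.3%) |
| 0.5 | 3.0% (3.2%) | 4.5% (5.6%) | 9.3% (10.0%) |
| 0.7 | 2.3% (1.9%) | 3.5% (4.1%) | 7.5% (7.8%) |

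Down each column, overlap lowers the rate. Across each row, uneven counts raise it. Single simulated cells are noisy: at f = 0.5, CV 0.5 the simulation falls above 5% and the formula below it.

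**4. What corrects it.** In the same simulation, SEs clustered on provider reject 4.2% to 5.8% throughout. Robust SEs that allow for uneven counts but ignore overlap reject 1.9%, 2.4% and 2.6% at f = 0.7 for CV 0, 0.5 and 1. Clustering on provider is therefore the part that repairs the overlap.

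**The case against.** **Overlap is inferred.** PE CALC was already in use when the Aim 1 interviews were due to start in January 2019, and in Section 9 "The pilot trial will end in June 2022". The launch and the end of the pilot are thus at least three years apart, and residents are eligible. This stands: overlap is probably partial and concentrated in attendings and physician assistants. It does not justify assuming none.

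**The overlap error is conservative and costs no stated power.** This also stands. At f = 0.5, r = 0.3 the SE is about 8% too large (1.155/1.065 = 1.08), a modest matter in a pilot. But the conservative direction holds only for overlap taken alone.

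**The high rejection rates come from uneven counts, not from shared providers.** Correct: they are worst with no overlap. They are shown because both errors act on the same planned test, so its net direction cannot be known in advance. A CV of 1 has no basis in the documents.

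**Step 3 reads the 10% SD as between-provider, while step 2 reads it as the total.** True: step 3 implies an observed SD of √(0.01 + 0.003917) = 11.8% at CV 0. Setting the total SD to 10% instead (B = 0.00595, W = 0.00405, between-provider SD about 7.7%) gives, by the same formula, 12.1% rather than 13.5% at f = 0, CV 1, and 2.8%, 3.8% and 7.1% at f = 0.7. The pattern is unchanged.

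**Covariate adjustment and subject codes partly help.** The regression adjusts for age, gender, race and provider type, which addresses some change in staff mix but not the SE. Section 20 assigns subject numbers, and Appendix A uses encrypted codes and destroys linkages only after final analyses. Linkage is therefore possible, but it is not planned.

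**Conclusion.** The concern holds and should be fixed. Every comparative test named for Aim 3 assumes independent groups, while the design makes shared providers likely. CTPA yield and ordering have no named test, and satisfaction is only described, so the point does not reach them.

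Taken alone, overlap inflates the SE. Type I error falls to between 3.4% and 1.5% for f of 0.5 to 0.7 and r of 0.3 to 0.5, and to 0.6% at the full-overlap bound with r = 0.5. For the weighted test as planned, error with overlap of 0.5 to 0.7 runs from about 2% to 10%, depending on the spread of encounter counts. The sizes rest on assumed overlap, correlation and encounter counts. The omission itself is plain in the text. The power claim survives.

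**What to change.** - Keep the encounter-weighted comparison and the weighted regression, but compute standard errors clustered on provider. A GEE with provider as the cluster serves equally well.
- Retain providers seen in only one period. A purely paired test would discard them.
- Carry a coded provider ID across both EHR extracts, and specify it before the linkages are destroyed.
- Report the number of providers in both periods, leavers and joiners, in place of the two-sample tests of provider characteristics.
- Add a sensitivity analysis restricted to providers present in both periods. This bears on staff turnover, which clustering alone does not address.
- Reconcile Section 24 with Section 12. The waiver request says "it involves collection of de-identified aggregate data from the EHR at the NSUH and LIJMC Emergency Departments", but the analysis already needs adoption rates, encounter counts and characteristics for each provider.

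The cost is small: revised wording in Section 12, one option in the planned regression, the coded link, and a correction of the waiver text with the IRB.
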